9.1.9 POST-EXPLANT VISIT & STUDY EXIT (IN-PERSON, day 42 +/- 2)

A Study Exit CRF must be completed for any subject who signed an informed consent form, as they are considered enrolled in the study. Data to be collected at this visit include study exit date and reason for study exit, device or procedure related AEs, technical observations/device deficiencies and surgical interventions.

Some scenarios may lead to study exit and require completion of a Study Exit CRF: These include subject ineligibility for the implant in the opinion of the study physician, failure to meet inclusion criteria, meeting exclusion criteria, removal of the SCS lead without re-implantation, attempted implant without SCS implantation, voluntary withdrawal by the subject, subject withdrawal by the investigator, failure to maintain adequate study compliance and/or subject death.

Assessments and Data Collection	Screening and Enrollment	Call for patch removal	Injectrode Placement	Follow-up visits	Efficacy and Explant visit	Post study follow-up
Day (relative vs. Placement)	-5 to -4	-2	0	7 ± 2 14 ± 2	28 (-2 to 0)	42 ± 2
● Eligibility confirmation	✓					
● Medical history	✓					
● Physical exam	✓					
● Informed consent	✓					
● Record demographics	✓					
● Verification of absence of allergy to gold & pregnancy test	✓					
● Confirmation of study eligibility	✓					
● Removal of skin patch		✓				
● Read skin test patch results			✓			
● Basmati placement procedure			✓			
● Ultrasound & Fluoroscopy image capture			✓		✓ (pre & post)	(✓)
● Capture of images of surgical site	✓		✓ (post)	✓ (✓)	✓	✓ (✓)
● Remove skin suture(s) if placed during surgery						
● Measure impedance needle to needle connection					✓	
● Measure stimulation thresholds					✓	
● Removal procedure					✓	
● Study participant exit						✓

Table 6: Focus on Post study follow-up

10.0 ADVERSE EVENT REPORTING

During the study, the investigator will determine whether any adverse events (AE's) have occurred. For the purpose of this protocol, an adverse event is any undesirable clinical occurrence in a subject that can be attributed to the device or incision closure procedure.

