Study Design and Scope	The proposed study is a prospective, single-center, single-arm, non-randomized design. Up to 10 study subjects will be provided with the placement of an Injectrode insert. The maximal placement duration will be 28 days. Subjects selected to participate in the trial are healthy without any preexisting condition indicated to be treated. Each subject will be followed during the trial period of approximately 50 days, including the time for screening and post-explant follow-up. The study will end when the last subject has completed the trial period and exited. After exit from the clinical study, subjects will continue to be followed by their physician per standard of care. All device and procedure-related adverse events (AEs) and unanticipated problems (UPs) will be collected and reported per the study protocol.
Planned Enrollment	We plan to enroll and screen up to 20 study participants, of which up to 10 participants will be provided with a Basmati Injectrode Insert for the trial.
Primary Safety Objective	Primary measures of device safety will include verification of the absence of unexpected inflammation and minimization of excessive encapsulation around the Injectrode as verified by cell staining and pathohistological analysis.
Secondary Effectiveness Objective	Secondary measures of device effectiveness will include impedance and stimulation threshold measurements for subcutaneous nervous tissue.

STUDY FLOWCHART

[figure not shown]

Table of Contents

	Page
PROTOCOL TITLE	I
PROTOCOL SYNOPSIS	II
FLOWCHART	III
TABLE OF CONTENTS	IV
LIST of ABBREVIATIONS AND DEFINITIONS	VI
INTRODUCTION	1
BACKGROUND AND RATIONALE	1
CURRENT TREATMENT APPROACHES AND SHORTCOMINGS THEREOF	1
CLINICAL NEED FOR A “LAST MILE CONNECTION” TO CONNECT TO A NERVE	2
RATIONALE FOR THE NON-SIGNIFICANT RISK CLASSIFICATION OF THIS STUDY	4
COMPARISON TO EARLIER STUDIES	5
STUDY PARTICIPANT SAFETY	6
PRE-CLINICAL DATA / SUMMARY OF PREVIOUS STUDIES	6
OBJECTIVES	7
PRIMARY OUTCOME MEASURES: SAFETY	8
SECONDARY OUTCOME MEASURES: INTERFACING EFFICACY	8
DEVICE	9
NEURONOFF BASMATI INJECTRODE INSERT	9
REGULATORY CLASSIFICATION	11
STUDY DESIGN	12
SCHEDULE OF EVENTS (SOE)	13
OUTCOMES	14
PRIMARY SAFETY OUTCOME MEASURES	14
SECONDARY SAFETY OUTCOME MEASURES	14
MINIMIZATION OF BIAS	15
INVESTIGATORS	16
INVESTIGATOR SELECTION AND RESPONSIBILITIES	16
STUDY POPULATION	17
INCLUSION CRITERIA	17
EXCLUSION CRITERIA	17
SAMPLE SIZE	18
METHODS AND PROCEDURE	19
DATA COLLECTION REQUIREMENTS	19

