4.0 STUDY DESIGN

The proposed study is a prospective, single-center, single-arm, non-randomized design. The study will screen up to 20 subjects for study eligibility and potential enrollment. Up to 10 study participants will be provided with the placement of a Basmati Injectrode insert. The maximal placement duration will be 28 days. Subjects selected to participate in the trial will be solely healthy volunteers without any preexisting condition indicated for treatment. Each subject will be followed during the trial period of approximately 45+/-2 days.

The study will end when the last subject has completed the trial period and exited. The expected enrollment period for this study is approximately 2 months. After exit from the clinical study, subjects will continue to be followed by their physician per standard of care. All device and procedure-related AEs and UPs will be collected and reported per the study protocol.

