All equipment will be turned on prior to use, followed by connecting the Stimulator in parallel to the Oscilloscope as shown in Figures 7a through 7e below. Data will be recorded for every measurement. Prior to beginning the measurements, test leads will also be hooked up to the stimulator in parallel. Generally, measurements during this visit will be recorded at a current amplitude ranging between 0.1 and 10 mA and pulse widths ranging from 50 μ sec to 1500 μ sec. Reference impedance values will be recorded at a current amplitude at 1mA and a pulse width of 200 μ sec using a reference resistor of 1 kOhm. The sensory stimulation thresholds ("Measurement 1" through "Measurement 3.3") below will be conducted with a preferred pulse width of 100 μ sec and 200 μ sec, and, if need be, may be measured once more with a different pulse width in the range between 50 μ sec to 1500 μ sec to be able to capture stable measurements.

In order to record sensory afferent nerve responses to electrical stimulation, it is imperative that lidocaine is not injected at the site of the Injectrode for the entity of part 1. Instead, the skin above the

Injectrode is cleaned using 70% Isopropyl alcohol at the site of the Injectrode with a margin of 3cm around the site, identified via palpation of the skin. Two 30 gauge needles are inserted through the cleaned skin into the Injectrode as shown in Figures 8a through 8e. At a location 1-2cm away from the Injectrode, a third 30 gauge needle will be inserted as shown in Figure 8a. Finally, at a location approximately 10 cm away from the Injectrode, a TENS patch electrode will be placed to function as the return electrode for electrical current. Test leads with hooked ends will be attached to the needle shaft extending out of the skin and taped to the skin to keep the leads secure and from pulling on the needles should the study participant or lead move.

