Measurement 1: Once the leads are properly attached to the needles and TENS patch, testing may commence. The first measurement will establish the stimulation activation (sensation) threshold of afferent nerves in the skin of the hip region of the study participant in the vicinity of where the Injectrode is present. Needle D and TENS patch C will first be connected to the stimulator (as shown in figure 8a), and step wise increments in stimulus amplitude will be performed until the study participant notes that they can perceive the stimulation (e.g. step size amplitude = 100 μ A, pulse width = 200 μ sec). The study participant will be asked to report when they perceive a paresthesia, essentially a tingling sensation of the skin. The current and pulse width values for the initial report of paresthesia will be recorded and may be verified with a second measurement. The values allowing the study participant to perceive a tingling paresthesia sensation are expected to be an order of magnitude smaller than currents needed to cause the perception of pain. If the study participant reports pain during the stimulation then the clinician will adjust their testing approach accordingly to avoid such participant feedback. Once the stimulation activation threshold is determined, lead D may be unplugged and needle D removed from the skin.

[figure not shown]

Figure 8a: Stimulus activation setup of electrodes for measurement #1.

A series of three stimulation tests will be performed between the Injectrode (A, B) and the TENS patch (C), as shown in Figures 8c, 8d, and 8e. The first stimulation for each measurement will be performed at or below the stimulation threshold established in measurement 1 for the study participant. The study participant will be asked whether they sensed the stimulus, and their answer recorded. If needed, the stimulation current will be increased in increments of 100 μ A of current or 50-100 μ sec of pulse duration until the study participant perceives the stimulus.

In **measurement 2** (Figure 8b), needle A and the TENS surface patch electrode (C) will be hooked up to the stimulator and oscilloscope.

[figure not shown]

Figure 8b: Impedance and Stimulation setup of electrodes for measurement #2.

In **measurement 3** (Figure 8c), needle B and the TENS surface patch electrode (C) will be hooked up to the stimulator and oscilloscope.

[figure not shown]

Figure 8c: Stimulation setup of electrodes for measurement #3.

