10.1 ADVERSE EVENTS

In this study, study participants should be encouraged to report AE's spontaneously or in response to general, non-directed questioning (e.g., "How has your health been since the last visit?") per Neuronoff SOP-38. Any time during the study, the study participant may volunteer information about any event that resembles an AE. If it is determined that an AE has occurred, the investigator should obtain all the information required to complete the AE Form of the CRF.

The following categories of adverse event severity are to be used:

Mild	Awareness of a sign or symptom that does not interfere with the study participant's usual activity or is transient, resolved without treatment and with no sequelae
Moderate	Interferes with the study participant's usual activity
Severe	Any fatal or immediately life-threatening clinical experience that requires a subject to be hospitalized, or hospitalization is unduly prolonged because of potential disability or danger to life or because an intervention has been necessitated. This includes events that cause fetal distress, fetal death, congenital abnormality or malignancy or any permanently disabling event.

Table 7: Categories of adverse event severity

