10.2 ANTICIPATED ADVERSE DEVICE EFFECTS

The following ANTICIPATED EVENTS have been identified as possible complications of participation in the study.

- Infection at implant site
- Pain at implant site
- Bleeding
- Bruising
- Itch
- Allergic reaction

To minimize the risk of any study participant developing an allergic reaction to the Basmati insert's sole material (gold of 99.99% purity), a gold skin test will be performed during the first study visit. Patients only advance to the implant visit after a negative skin allergy test to gold has been confirmed.

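### Section 10.0 limits adverse events to the device or incision closure, while the synopsis, 4.0 and 9.1.9 cover all device- and procedure-related events

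*Protocol*

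**What the plan says.** Section 10.0 gives the working definition for the whole protocol: "an adverse event is any undesirable clinical occurrence in a subject that can be attributed to the device or incision closure procedure". Section 10.1 then ties recording to that decision: "If it is determined that an AE has occurred, the investigator should obtain all the information required" for the AE Form.

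Three other places describe a different scope:

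- Synopsis, Study Design and Scope: "All device and procedure-related adverse events (AEs) and unanticipated problems (UPs) will be collected and reported per the study protocol".
- Section 4.0: "All device and procedure-related AEs and UPs will be collected and reported per the study protocol".
- Section 9.1.9, on the data due at study exit: "device or procedure related AEs, technical observations/device deficiencies and surgical interventions".

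Section 10.2 introduces its list of expected events in broad terms as well: "The following ANTICIPATED EVENTS have been identified as possible complications of participation in the study".

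**The concern.** Closing the incision is one step, done at the end of placement (9.1.6) and again after explant (9.1.8). The study does much more to its volunteers: a gold patch test, local anesthesia, a scalpel incision with blunt dissection, needle insertion with electrical stimulation, and a Mohs-style removal. An event due only to one of these belongs in the record under the synopsis, 4.0 and 9.1.9, but is not an AE under 10.0.

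The narrow wording sits where the investigator has to apply it. The synopsis and 4.0 defer to the protocol for how events are collected and reported, which leads back to section 10. Two careful readers could therefore treat the same event differently on the AE Form. This is a first-in-human study (11.2) whose main purpose is safety, and a second study with deeper placement is meant to build on it (1.3, 1.4). Its AE record should have one scope.

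**Working it through.** No formula applies to the contradiction itself, so the check sets the texts side by side.

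**Step 1: compare the scopes.**

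| Place | Source of harm covered |
|---|---|
| 10.0 (definition) | device; incision closure |
| Synopsis | device; procedure |
| 4.0 | device; procedure |
| 9.1.9 (exit data) | device; procedure |
| 10.2 (anticipated events) | taking part in the study |

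**Step 2: does procedure mean closure elsewhere?** It does not. The schedule of events (4.1) names a placement procedure and a removal procedure, and 9.1.6 and 5.0 use the word for the insertion and the explant. The closure-only phrase occurs only in 10.0, and no section says that it stands for study procedures in general.

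**Step 3: which events fall between the two scopes?** The clearest cases are harms that involve neither the device nor closure.

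- *Remote needle (9.1.8, Part I).* "At a location 1-2cm away from the Injectrode, a third 30 gauge needle will be inserted", and for the first measurement "Needle D and TENS patch C will first be connected to the stimulator". This circuit runs between needle D and the surface patch. Needles A and B enter the Injectrode, so harm from them could be argued to be device-related. They are not relied on here.
- *Local anesthetic.* It is given at placement (9.1.6) and at explant (9.1.8, Part II). Exclusion criterion 19 in 8.2 shows that the protocol recognizes reactions to it.
- *Gold patch test (9.1.3, 9.1.6).* It comes before any device. Under 9.1.2 a person is an enrolled subject from consent, and 9.1.9 requires an exit form for everyone who consented. A subject who is never implanted has neither device nor closure, so under 10.0 read literally this person cannot have an AE. A positive reading is already recorded as the test result (8.2, 9.1.6), so only harm beyond that reading is meant.

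**Step 4: exposure caps.** Inputs: up to 20 screened and up to 10 implanted (4.0, 8.0).

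- Needle D: 1 per implanted subject × 10 = up to 10.
- Local anesthetic: 2 occasions × 10 = up to 20.
- Patch test without device: 20 − 10 = 10 if both caps are reached. The number is lower if some fail screening before the patch is placed, and higher if fewer than 10 are implanted.

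These count exposures, not misclassified events. The protocol gives no event probabilities, so no effect on an AE rate follows.

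**The case against.** The strongest reply is that the wording in 10.0 is merely loose and that the rest of the protocol catches nearly everything. Section 10.2, in the same chapter, lists infection, pain, bleeding, bruising, itch and allergic reaction without restricting them to closure. Section 5.0 has CRFs for any pain or discomfort and for unanticipated problems. The exit form asks for procedure-related AEs from everyone who consented. Table 9 sends deaths to the sponsor and the IRB without an attribution test, and Table 8 does not separate device from procedure. AE elicitation follows SOP-38, which is not shown and, like the AE Form, may already be wider. AE frequency is not a named primary or secondary measure. Finally, the word procedure is undefined in the wider passages, so including a screening patch test is an inference.

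Much of this stands as a limit on the consequence. What remains is mainly a non-fatal event due only to a procedure, which is not pain or discomfort, not on the 10.2 list and not an unanticipated problem. Even that might be recorded in practice.

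It does not remove the contradiction. The 10.2 list shows that a wider scope was probably intended, but it does not amend the definition. The exit form itself uses the term AE, which 10.0 defines narrowly. An SOP outside the protocol cannot make the protocol agree with itself. Counting the patch test as a study procedure is reasonable, given that consented screenees are enrolled subjects who need an exit form.

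**Conclusion.** The concern holds. Section 10.0 states a narrower AE scope than the synopsis, 4.0 and 9.1.9, and it is the section that controls use of the AE Form. That mismatch is certain from the text and should be fixed. The practical consequence is limited: inconsistent recording on one form of harms due only to a study procedure other than closure.

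This conclusion assumes that 10.0 is applied as written and that procedure in the other sections has its ordinary meaning. How far data would be lost depends on SOP-38 and the AE Form, which were not available. The histopathology primary measure (2.1, 5.1) is unaffected.

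**What to change.** In 10.0, keep the definition up to the mention of the device and replace the closure phrase with: *or to any study procedure (gold patch test, local anesthesia, placement, needle and stimulation measurements, explant, wound closure)*. Have the synopsis, 4.0 and 9.1.9 refer to this one definition. Then check that Tables 8 and 9, SOP-38 and the AE Form use the same scope. Table 9 needs particular attention, because its rows are death, unanticipated adverse device effects and other adverse device effects, and none is labelled for a non-fatal event due only to a procedure.

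The cost is one sentence, three cross-references and a check of two tables, one SOP and one form. The study may complete a few more AE forms and report a slightly less favorable AE count. The change concerns what is recorded, not how any subject is managed.

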10.1 ADVERSE EVENTS

In this study, study participants should be encouraged to report AE's spontaneously or in response to general, non-directed questioning (e.g., "How has your health been since the last visit?") per Neuronoff SOP-38. Any time during the study, the study participant may volunteer information about any event that resembles an AE. If it is determined that an AE has occurred, the investigator should obtain all the information required to complete the AE Form of the CRF.

The following categories of adverse event severity are to be used:

Mild	Awareness of a sign or symptom that does not interfere with the study participant's usual activity or is transient, resolved without treatment and with no sequelae
Moderate	Interferes with the study participant's usual activity
Severe	Any fatal or immediately life-threatening clinical experience that requires a subject to be hospitalized, or hospitalization is unduly prolonged because of potential disability or danger to life or because an intervention has been necessitated. This includes events that cause fetal distress, fetal death, congenital abnormality or malignancy or any permanently disabling event.

Table 7: Categories of adverse event severity

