In the proposed safety study, the Basmati insert will be used as a passive device not intended for diagnosing, curing, mitigating, or treating disease, or otherwise preventing impairment of human health. Prior to removing the device in a minimally invasive procedure, the Injectrode will be briefly interfaced with electrical current using standard electro-acupuncture techniques, following the labeling for these approved devices. The total time of exposure to this limited stimulation period will be approximately 20 minutes right prior to device extraction via Mohs procedure.

- 4. Otherwise presents a potential for serious risk to the health, safety, or welfare of a subject.**

Based on the Neuronoff, Inc. Quality Management System, risks associated with the device will be evaluated and addressed per the Design Control Procedure, SOP-02 and the Risk

Management Procedure, SOP-05 and according with the ISO-14971 Risk Management Standard to assure that the Basmati Injectrode insert is deemed to not represent any potential for serious risk to the health, safety, or welfare of a subject. The minimally invasive placement at a location in the subcutaneous tissue and rigorous follow-up schedule are designed to allow the physician to monitor the response of each study participant very closely and, if necessary, explant the device prior to the 28 day mark without unnecessary risk to the health, safety, or welfare of a subject. The material of the Injectrode is 99.99% gold, a material commonly used in neuromodulation electrodes that is biointert and very well received by humans clinically. The method of removing the Injectrode at the end of the safety study will follow a procedure similar to a Mohs procedure, a standard clinical practice that poses little risk to study subjects. Subjects will be followed for signs of inflammation of the surgical site, granulomas, irritation.

This early feasibility study aims to document the clinical biological response to an Injectrode, roughly the size of a Basmati rice grain, placed temporarily into up to 10 healthy volunteers for a duration of up to 28 days. The efficacy of the device is assessed by measuring electrical and sensory nerve recruitment data immediately prior to explanting the device. These data are intended to provide rationale for a follow-up study testing a therapeutic intervention.

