5.0 OUTCOMES

The outcomes of the study are focused on collecting data to determine clinical outcomes of placing the Basmati Injectrode for up to 28 days in healthy study participants to 1) assess tissue responses and, on the last day just prior to explant, 2) collect data describing the quality of the electrical interfacing with the Injectrode from outside of the body, as well as with subcutaneous sensory nerves surrounding the Injectrode insert.

Safety data will also be collected at all visits. Data will be collected using:

- True color images of the surgical site and the insert placement location.
- Ultrasound and fluoroscopy (x-ray) images of the insert placement location.
- CRFs to capture any pain or discomfort, AEs and UPs.
- Patho-histological data from tissue samples collected during the explant procedure (Injectrode with approximately 0.5 to 1mm of naïve tissue in Mohs style procedure).

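### Section 10.1 relies on undirected questioning although six local effects are named in advance, and the promised pain capture has no schedule row or scale, so pain and itch may be under-recorded

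*Protocol*

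**What the plan says.** On asking about harms, section 10.1 states one approach: participants are encouraged to report adverse events "spontaneously or in response to general, non-directed questioning". The example given is "How has your health been since the last visit", and SOP-38 is cited as the governing procedure.

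On which harms are expected, section 10.2 lists six: infection at the implant site, pain at the implant site, bleeding, bruising, itch and allergic reaction. They are introduced as events that "have been identified as possible complications of participation in the study". Section 1.4 adds: "Subjects will be followed for signs of inflammation of the surgical site, granulomas, irritation".

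On what will be collected, section 5.0 says "Safety data will also be collected at all visits". The listed means include "CRFs to capture any pain or discomfort, AEs and UPs" and "True color images of the surgical site and the insert placement location", together with ultrasound, fluoroscopy and histology.

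On timing, the schedule of events in section 4.1 and its repeats in section 9.1 have a row for site images but none for adverse events, pain or local symptoms. The heading of section 9.1.7 allows the day 7 and day 14 follow-ups to be in person or by call. Section 9.1.9 lists device- or procedure-related adverse events among the data taken at the exit visit.

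**The concern.** The protocol knows which local effects to look for and says that pain or discomfort will be captured, but its only stated way of asking is an undirected one. An open question leaves it to the participant to decide whether a sore or itchy site is worth mentioning. Nothing in the schedule prompts the site to ask, and no scale, recall period or checklist is given.

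What is at stake is the descriptive safety summary. Safety is the leading objective, at most 10 people receive the device, and there is no control arm. One or two events not recorded would visibly change a table of that size, and a zero in it could not be read as evidence that the effect did not occur. The loss cannot be made good later: mild symptoms not asked about at day 7 or day 14 cannot be reliably reconstructed at exit.

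**Working it through.** The plan gives no adverse event rate, power statement or sample-size formula, so there is no figure to reproduce. The check has two parts.

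**1. Which effects rest on the open question?**

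- *Pain and itch.* Photographs, ultrasound and fluoroscopy cannot show them. The remaining routes are the question in section 10.1 and the CRF item for pain or discomfort in section 5.0, for which the protocol gives no prompt or scale. Itch is not named in that CRF item.
- *Infection, bleeding, bruising and visible allergic reaction.* At an in-person visit these can be seen and photographed. If day 7 or day 14 is a call, inspection by the investigator is not assured, and the protocol does not say how the site image is then obtained.
- *Recall.* After day 14 ± 2 the next scheduled contact is explant at day 26 to 28. The gap is 26 − 16 = 10 days at the shortest and 28 − 12 = 16 days at the longest. One open question may have to cover that period.

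**2. What could imperfect capture do?** Illustration only.

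Inputs: n = 10 (section 8.3). The true rate p and the share of cases captured c are assumptions; neither is in the protocol.

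Expected number recorded = n·p·c. For p = 0.5:
- full capture: 10 × 0.5 × 1 = 5
- c = 0.8: 10 × 0.5 × 0.8 = 4
- c = 0.4: 10 × 0.5 × 0.4 = 2

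Chance of recording none = (1 − p·c)^10. For p = 0.2:

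| Capture c | p·c | Chance of 0/10 |
|---|---|---|
| 1.0 | 0.20 | 0.80^10 = 10.7% |
| 0.8 | 0.16 | 0.84^10 = 17.5% |
| 0.5 | 0.10 | 0.90^10 = 34.9% |
| 0.4 | 0.08 | 0.92^10 = 43.4% |

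Put the other way, the chance of recording at least one case of a 20% effect falls from 89.3% with full capture to 65.1% at c = 0.5.

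A zero is weak evidence even with full capture. The exact two-sided 95% upper limit for 0/10 is 1 − 0.025^(1/10) = 30.8%. That limit applies to the recorded rate p·c. For the true rate it must be divided by c, giving 0.3085/0.8 = 38.6% at c = 0.8 and 0.3085/0.4 = 77.1% at c = 0.4.

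**The case against.** A reader might infer that open questioning is the only route by which local harms are found. The protocol does not support that. Section 5.0 provides site images and a CRF item for pain or discomfort, section 1.4 has subjects followed for inflammation, granulomas and irritation, section 10.0 has the investigator determine whether an adverse event occurred, and section 9.1.9 collects adverse events at an in-person exit visit. Visible effects are therefore partly covered. This stands, and it confines the point to pain and itch, plus visible effects when the contact is a call.

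A reader might also infer that rates *will* be under-counted. That goes too far. SOP-38 and the case report form (SOP-36-F3) are listed in section 18.1 but are not shown, and either may hold prompts or a pain field. The pain item in section 5.0 and the adverse event wording in section 10.1 can coexist. This stands in part. However, section 10.1 cites SOP-38 as the basis for undirected questioning, so directed prompts on the form would sit awkwardly with it, and the sections would still need to be aligned.

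Third, no adverse event rate is an endpoint. The primary outcome is histological, and section 11.2 says the study is not powered. This stands: the effect is on a descriptive table, not on a test.

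Fourth, undirected questioning is a legitimate choice because it avoids suggesting symptoms. A checklist in a single-arm study will pick up ordinary post-incision soreness and bruising with no control to set it against. That is a real cost, and the reason to keep the open question first and report solicited events separately. It does not explain how the promised pain data will be obtained.

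The abbreviation list defines a Numeric Rating Scale that the text shown never uses. This may be template residue and carries no weight here.

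**Conclusion.** The point holds in a limited form. The protocol names six local effects and promises capture of pain or discomfort at all visits, but states only undirected elicitation and gives no schedule row, checklist or scale. Pain and itch, and visible effects when day 7 or day 14 is a call, may be under-recorded in the safety summary.

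The amount cannot be derived from the protocol. The rise in the chance of 0/10 from 10.7% to 17.5–43.4% rests on an assumed true rate of 20% and an assumed capture of 40–80%. It applies to effects that depend on being asked about, not to all local effects alike. It also presumes that the unseen CRF and SOP-38 add no prompts; if they do, the remaining fault is that section 10.1 and the schedule do not say so.

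The documents do not support reading this as a threat to the primary outcome, or as showing that local tolerability rates are a main output of the study. It is a cheap improvement to make before the first placement.

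**What to change.** - In section 10.1, keep the open question first, so that unprompted events are recorded before anything is suggested.
- Then, at each contact from day 0 to exit, including calls, ask yes/no about each of the six effects in section 10.2 and record a 0–10 implant-site pain score.
- Add one row for this to the schedule in section 4.1 and to its repeats in section 9.1, and align the CRF and SOP-38 with it.
- Report solicited and unsolicited events separately.

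Cost: one CRF page and one or two minutes per contact. With five contacts (day 0, day 7, day 14, explant, exit) and 10 participants, that is 5 × 10 = 50 checks, or about 50 to 100 minutes over the whole study. No extra staff, visits or procedures are needed. The downside is a higher count of mild events, which separate reporting makes plain.
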